# 4.2. Discontinuation of Study Treatment and Participant Discontinuation/Withdrawal

### 4.2.1. Discontinuation of Study Treatment

All subjects are encouraged to stay in the study regardless of study treatment discontinuation. Any subject who discontinues from the study treatment will have the reason for discontinuing treatment recorded and will be encouraged to continue to attend the remaining scheduled study visits and to complete patient-reported outcome measures assessed between study visits (Table 5, Section 7.5).

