Except for those subjects who withdraw consent, die, or are lost to follow-up, subjects who discontinue their assigned study drug will be encouraged to continue to participate in their remaining scheduled study visits. Every effort should be made by the Investigator to keep these subjects in the study through Visit 11. "Lost to follow-up" should be marked only in an exceptional case when all documented attempts to reach the subject by the Investigator or other staff members were unsuccessful.

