### **4.2.2.2.** Early Discontinuation Procedures

If a subject prematurely discontinues the study, the subject will have:

• An EOT Visit; however, the Investigator should contact the medical monitor to determine if the EOT CT assessment will be needed for subjects in the CT scan substudy.

If a subject withdraws from the study, the Investigator will complete and report the observations as thoroughly as possible up to the date of withdrawal including the date of last treatment and the reasons for withdrawal.

If the subject is discontinued from the study due to an AE, the Investigator will follow the subject as described in Section 9.10 and Section 9.12.

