PGI-S q		X					Compl	ete every 2 v	veeks			
PGI-C q							Compl	ete every 2 v	veeks			
EQ-5D-5L/ QOL-PCD – Completion at site r		X	X		X		X		X		X	X
Blood PK samples 		X	X		X		X		X		X	
Sputum PD sample t	X	X	X		X		X		X		X	X
For substudy only: blood PD u	X	X	X		X		X		X		X	X
Health resource utilization V			X	X	X	X	X	X	X	X	X	

Study Period	Screen		Treatment Period									Follow-Up
Study Days Study Weeks	Days -42 to -1	D1 (Baseline)	D28 Wk4	D70 Wk10	D112 Wk16	D154 Wk22	D196 Wk28	D238 Wk34	D280 Wk40	D322 Wk46	D364 Wk52 (EOT or E/D) a	D392 Wk56 (EOS)
Visit	V1	V2	V3	Phone V4 b	V5	Phone V6 b	V7	Phone V8 b	V9	Phone V10 b	V11	V12
Collect days of work/ school missed			X	X	X	X	X	X	X	X	X	
Dispense study drug, accountability of returned drug, and review of dosing diary W		X	X		X		X		X		X w	X w
Adverse events collection		X	X	X	X	X	X	X	X	X	X	X
Assessment of skin conditions (hyperkeratosis of palm and soles) x		X	X		X		X		X		X	X
Assessment of periodontitis y		X	X	X	X	X	X	X	X	X	X	X

Note: for each of the Study Visits from Visit 3 to End of Study (Visit 12), there is a ±7-day window.

<sup>a Visit 11 (Week 52) is completed for those who finish study treatment per protocol. The visit is alternatively completed for those who discontinue early from study treatment.

b For Phone Visits, collect data outlined in Phone Visit Sheet: exacerbations, safety events, hospitalizations, or emergency room visits (including start and end date, follow-up with facility to retrieve source documentation), days of work missed (including start and end date), IV antibacterial drug use (including start and end dates), list of new rescue medications (including name, and start and end dates).

<sup>c Demographics and medical history: At Visit 2 (Baseline) only medical history collected.

<sup>d Height, weight, and BMI: Body weight will be measured at Screening and at the Week 52 (Visit 11; EOT). For adult subjects, the measurement of height, without shoes, will be performed at Screening Visit only. For adolescent subjects, measurement of height, without shoes, will be performed at Screening Visit and Visit 11 (EOT).

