## 7.3. Pulmonary Function Tests

Pulmonary function tests include the following: pre- and postbronchodilator  $FEV_1$ , pre- and postbronchodilator  $ppFEV_1$ , FVC, FEF(25-75%), and PEFR.

Pre- and postbronchodilator PFT by spirometry (FEV1, ppFEV1, FVC, PEFR, and FEF[25-75%]) will be performed per the ATS/ERS criteria (Miller et al., 2005) at Visit 1 (Screening), Visit 2 (Baseline), Visit 5 (Week 16), Visit 7 (Week 28), Visit 9 (Week 40), and Visit 11 (Week 52) (Table 5). Subjects should be provided with detailed instruction on how to conduct the FVC maneuver per ATS/ERS spirometry standardization before performing the test.

Subjects should be advised to withhold short-acting inhaled drugs (eg, the  $\beta$ -agonist albuterol/salbutamol or the anticholinergic agent ipratropium bromide) within 6 hours prior to the test. Long-acting  $\beta$ -agonist bronchodilators (eg, salmeterol or formoterol) or long-acting muscarinic bronchodilators (eg, tiotropium) or oral therapy with aminophylline or slow release  $\beta$ -agonists should be withheld for 12 to 24 hours depending on the medication used (refer to Table 4 for the minimum time intervals for a list of restricted medications) prior to the testing.

In the event a subject has taken a restricted medication during the specified time interval before the test, the test should be rescheduled for another visit within the protocol-specified visit window. If rescheduling the visit is not feasible for the subject, the test should be conducted as usual with appropriate notation in the source documents.

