### 6.4.9. Data Re-allocation for Early Discontinued Participants

Data collected at multiple visits (spirometry, smoking status, vital signs, and laboratory data) recorded at the EOT visit (Week 52, Visit 11) for early discontinued participants will be reallocated. Re-allocation will depend on the actual date of the EOT visit and the closest expected (scheduled) visit date.

For example, if the last visit performed before the EOT visit is Visit 4, the data recorded at the EOT visit will be re-allocated to Visit 5 or 6 depending on the date of the study termination visit. If the study termination visit was performed less than 7 days after the preceding visit, e.g., if the EOT visit was performed in the same visit window as defined in Section 6.5, data other than PEs/AEs/SAEs/AESIs recorded at the EOT visit will not be re-allocated and they will be excluded from the statistical analysis, summary tables and figures. For each assessment, only the visits at which the assessment was scheduled per CSP will be considered for re-allocation. This means that vital signs and laboratory data can be re-allocated to Visits 3, 5, 7 and 9 only. Visit windowing as defined in Section 6.5 will be considered for allocation of data.

Assessments completed every 2nd week, e.g., PGI-S, PGI-C, and QoL-B, will not be reallocated.

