## 6.6. Reporting of Data After Early Discontinuation of IP

All participants who discontinued IP early are encouraged to stay in the study for continued assessments following the same study procedures until the EOS. Reasons for early IP discontinuation will be recorded. If a participant withdraws consent from continued monitoring, the EOS visit will be completed.

The purposes for collecting these data are to permit full efficacy data ascertainment per the ITT principle in accordance with the On-Study estimand and to allow continual monitoring of participant safety for the 4-week follow-up period after IP discontinuation.

Reporting rules for data collected after early discontinuation of IP are outlined for each data type (efficacy, safety, pharmacokinetic, pharmacodynamic, etc.) per the corresponding estimand, specifically the ICE handling strategy.

Safety data that are excluded from treatment emergent period, i.e., data collected after the 4-week follow-up post early discontinuation of IP, will be reported separately and will include basic summaries of:

- AE, SAEs and AESIs, (non-treatment emergent)
- Laboratory
- Concomitant medication.

Other collected safety data will be listed.

CONFIDENTIAL Page 37 of 139

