<sup>2 Note: The Week 52 visit is the EOT visit per CSP and the date is determined through the eCRF form "V11 (EOT or E/D)". The date of last IP administration will be determined through eCRF form "End of Treatment" as indicated in Section 6.4.2. Participants who complete IP and the Week 52 visit as per protocol the on-study and on-treatment estimand will select the same data for analysis. Participants who discontinue from IP early, the date of Week 52 visit will be calculated as MINIMUM(date of EOS, date of randomization + 363) to match the scheduled date of Week 52 to keep similarity across participants discontinuing the study early.

EOS date to calculate the time at risk. Participants ongoing at time of primary analysis, e.g., adolescents, the date of cut-off will be used as PE end date.

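### Table 5 footnote a allows Visit 11 to be used up when study drug stops, so Week 52 spirometry is intended but not secured for participants who stop drug and stay on study

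*Protocol*

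**What the plan says.** **When Visit 11 is done.** In Protocol 6.1, Table 5, Visit 11 is the Week 52 visit and its column is also marked for early discontinuation. Footnote a adds: "The visit is alternatively completed for those who discontinue early from study treatment". Protocol 4.2.2.2 has a different trigger for the early end-of-treatment visit: "If a subject prematurely discontinues the study, the subject will have" that visit. Protocol 4.2.2.1 likewise has people who withdraw from the study complete the Week 52 procedures. Table 5 footnote i speaks of leaving the study when it discusses the early end-of-treatment CT scan.

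**What is asked of people who stop drug.** Protocol 4.2.1 says they "will be encouraged to continue to attend the remaining scheduled study visits". Protocol 4.2.2.1 says: "Every effort should be made by the Investigator to keep these subjects in the study through Visit 11". SAP 6.6 says: "All participants who discontinued IP early are encouraged to stay in the study for continued assessments following the same study procedures until the EOS", and gives complete efficacy data for the On-Study estimand as one of its purposes. SAP 9.14 also has them continue with their remaining visits.

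**Where spirometry sits.** Protocol 7.3 schedules it at Screening, Baseline, Weeks 16 and 28, "Visit 9 (Week 40), and Visit 11 (Week 52"). Visit 12 (Week 56) has none.

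**How the SAP treats Visit 11.** Footnote 2 in SAP 6.7.1 takes the Week 52 date from the single Visit 11 form for those who complete treatment. For those who do not, it says: "Participants who discontinue from IP early, the date of Week 52 visit will be calculated as MINIMUM(date of EOS, date of randomization + 363"), which is the earlier of the end-of-study date and Day 364. SAP 6.4.9 says that spirometry and some other data "recorded at the EOT visit (Week 52, Visit 11) for early discontinued participants will be reallocated" to the nearest scheduled visit.

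**The concern.** Footnote a makes stopping treatment the trigger for an early Visit 11, and presents that use as an alternative to the Week 52 use, not an addition to it. The other passages make leaving the study the trigger. The two agree for someone who stops drug and leaves on the same day. They part for someone who stops drug and stays, which is the participant whose data a treatment-policy estimand most needs.

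Change in post-bronchodilator FEV1 at Week 52 carries hypotheses H7 and H8 in the multiplicity procedure (SAP 6.3.1). Its primary estimand uses treatment policy for early discontinuation of study drug (SAP Table 2). If Visit 11 is spent at drug stop, the Week 52 value is missing for a reason the plan created. The exacerbation and QoL-B endpoints are less exposed: the former can use the calculated Week 52 date and the latter a two-weekly diary. FEV1 needs a clinic visit with a spirometer.

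**Working it through.** The plan states no figure on this point, so the check is mainly a cross-reading.

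**Step 1. Trigger for an early Visit 11.**

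| Place | Trigger or instruction |
|---|---|
| Protocol Table 5, footnote a | Stopping study treatment |
| Protocol 4.2.2.1, on withdrawal | Leaving the study |
| Protocol 4.2.2.2 | Leaving the study |
| Protocol Table 5, footnote i (CT) | Leaving the study |
| Protocol 4.2.2.1, on stopping drug | Stay through Visit 11, so Visit 11 still lies ahead |

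Footnote a stands alone. No passage says that Visit 11 is done at drug stop and then again at Week 52.

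**Step 2. What remains if footnote a is followed literally.** Take a participant who stops drug between Weeks 28 and 40 and stays. Visit 11 is completed at drug stop. Visit 9 still gives Week 40 spirometry, off drug. The next scheduled spirometry would have been Visit 11, which has been used, and Visit 12 has none. The last FEV1 value is at Week 40.

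**Step 3. Whether a Week 52 value would be used if obtained.** The protocol window is Day 364 ± 7, that is Day 357 to 371. The SAP 6.5 interval for Week 52 is Day 344 to 378, which contains it. Spirometry done on time would be windowed to Week 52, and SAP 6.2 uses all observed data whether or not the participant is on drug. If that test had to be recorded outside Visit 11, its route into the analysis is less certain. SAP 6.5 sets out to use unscheduled data to fill nominal visits, SAP 6.1 keeps unscheduled data out of summaries except for baseline, and SAP 6.7.3 excludes optional lung function tests from all analyses.

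**Step 4. What replaces a missing value.** The repeated-measures model (SAP 8.3.3.1) and the imputation model (SAP 8.3.3.2 and Appendix I) have no term for being on or off drug. A missing off-drug value at Week 52 is therefore predicted from the participant's own earlier visits and from an arm made up largely of people still on drug.

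**Step 5. Bounds.** Let d be the fraction stopping drug and D the on-drug difference from placebo. The documents give no value for d; 10–20% is assumed. Suppose the effect is wholly lost on stopping, and no one who stops has any off-drug FEV1.

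- The treatment-policy difference is (1 − d)D, while the missing-at-random estimate stays near D.
- Overstatement = 1/(1 − d) − 1. At d = 0.10 this is 1/0.90 − 1 = 0.111; at d = 0.20 it is 1/0.80 − 1 = 0.250.
- Standard-error inflation, with no borrowing from earlier visits = 1/√(1 − d) − 1. At d = 0.10 this is 1/√0.90 − 1 = 0.054; at d = 0.20 it is 1/√0.80 − 1 = 0.118.

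The fraction that matters here is smaller than d: those who stop drug, stay on study and miss Week 52 spirometry because of this wording. The documents give no rate for that group. If it is near zero, so is the effect.

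**The case against.** A reader might infer that participants who stop drug have no planned Week 52 spirometry and that the FEV1 endpoint is unmeasured in them. The documents do not support that. Protocol 4.2.1 and 4.2.2.1 and SAP 6.6 and 9.14 all ask them to attend their remaining visits, and Visit 11 at Week 52 carries spirometry. Footnote a does not say that Week 52 is then skipped.

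The SAP passages can also be read more mildly. Footnote 2 in SAP 6.7.1 belongs to the time-at-risk rules for exacerbations and says nothing about whether spirometry is done. The last-dose date comes from a separate end-of-treatment form, so recording drug stop does not by itself consume Visit 11. The example in SAP 6.4.9 speaks of study termination, which suggests that re-allocation was meant for those leaving the study. Those who stay contribute their own off-drug Week 16, 28 or 40 values where these fall after drug stop. If the main result is significant, a two-way tipping-point analysis tests the missing data.

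All of this stands against the stronger reading. It does not tell a site what to do at Week 52 when Visit 11 has already been completed. A calculated Week 52 date, used for drug-stoppers in SAP 6.7.1 and again in 8.2.3 for those who stay, fits a plan in which their Visit 11 date cannot be relied on to fall at Week 52. The tipping-point analysis probes missing values but does not recover them.

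**Conclusion.** The inconsistency is real and worth correcting. The documents intend Week 52 follow-up in participants who stop drug and stay, but they do not secure Week 52 spirometry, and footnote a read literally can displace it. The consequence is a risk of avoidable missing Week 52 FEV1 in the treatment-policy analysis of H7 and H8, filled under missing at random largely from on-drug data. That would move the estimate towards the effect had everyone stayed on drug.

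The size cannot be estimated from the documents. The 11–25% overstatement and 5–12% standard-error inflation are upper bounds. They rest on an assumed 10–20% stopping drug, complete loss of effect, no off-drug FEV1 values, and every such participant missing Week 52 spirometry. Participants who leave the study lack the value whatever footnote a says, so only the share who stay is recoverable. Whether the eCRF accepts Visit 11 twice cannot be seen from the documents.

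**What to change.** **Protocol.** Reconcile footnote a with 4.2.2.1 and 4.2.2.2: use Visit 11 early only for participants leaving the study, record assessments made at drug stop under a separate visit label, and keep Visit 11 with spirometry at Week 52 for everyone still on study.

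**SAP.**
- State in 6.4.9 that re-allocation applies to participants who left the study.
- Reconcile 6.1 with 6.5 so that any acceptable spirometry on Day 344 to 378 counts as Week 52 FEV1, and say that a Week 52 test after drug stop is not an optional test under 6.7.3.
- Report by arm how many participants who stopped drug and stayed have Week 52 spirometry.

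**Cost.** Footnote and SAP wording, plus one visit label, subject to how the eCRF is built. No visit is added, because Week 52 is already among the visits these participants are asked to attend. Spirometry already missed cannot be recovered, but the SAP rules can be settled at the blinded data review before database lock.

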#### **6.2.** Protocol Deviations

The Investigator should conduct the study in compliance with the protocol as agreed to by Sponsor and, if required, by the regulatory authority(ies), and which was given approval/favorable opinion by the IRB/IEC.

The Investigator should notify the IRB/IEC of deviations from the protocol in accordance with local procedures.

As of May 2020, due to concern regarding COVID-19, there may be restrictions to subject attendance at in-clinic visits. In the event subjects are restricted to attend in-clinic visits, or if the subject has concern regarding travel and attending in-clinic visits (due to potential public health concerns), the site should contact the Sponsor on how to conduct the scheduled assessments, and decisions should be documented in the source documentation. Where necessary, in-clinic visits may be conducted via telemedicine link and home health care visits.

## **6.3.** Public Health Emergency Situations

During the COVID-19 public health emergency, the Sponsor, IRB/IECs, and Investigators shall follow the most current version of local guidance to assure the safety of study subjects, maintain compliance with GCP, and minimize risks to study integrity. In anticipation that the COVID-19 pandemic may have an impact on the conduct of clinical studies, the Sponsor does not intend to screen any new subjects in this study unless the impact of the COVID-19 pandemic is deemed manageable and no longer interfering with the conduct of the study at individual sites, and subjects can safely participate in this study. The continuity of clinical study conduct and oversight may require implementation of temporary or alternative mechanisms, which will remain in effect only for the duration of the local public health emergency. Examples of such mechanisms may include, but are not limited to, any of the following: telephone contact, virtual visits, telemedicine visits, online meetings, non-invasive remote monitoring devices, use of local clinic or laboratory locations, and home visits by skilled staff. The site should contact the Sponsor on how and when to implement temporary and/or alternative mechanism of scheduled assessments, and all decisions taken should be documented in the source documentation. Additionally, all temporary mechanisms utilized, and the resulting deviations from planned study procedures are to be documented as being related to COVID-19.

In a situation where local health authorities declare a public health emergency while the trial is ongoing, the suggested guidance in the following subsections should be followed.

### **6.3.1.** Continuation or Suspension of the Study

Ensuring the safety of trial participants is paramount. The Sponsor (Insmed Incorporated), in consultation with clinical Investigators and IRB/IEC, will determine if the protection of a participant's safety, welfare, and rights are best served by continuing or stopping the trial at the specific site. Such decision will depend on specific circumstances, including the ability to conduct appropriate safety monitoring, the potential impact on the investigational product supply chain, and other considerations.

If the decision is to continue the study, the following considerations will be taken into account.

### **6.3.1.1.** Study Recruitment

The Sponsor will communicate to the sites the decision on whether to continue or suspend recruitment after considering the specific circumstances of each site, recommendation by the IRB/EC, and its local health authority mandates. If, due to COVID-19, study discontinuation exceeds the assumed rate, the Sponsor may allow enrollment past the assumed sample size.

#### 6.3.1.2. Subjects Already Enrolled in the Study

If the decision is to continue the participation of subjects already enrolled, the following steps should be taken:

- If a subject is not able to complete a protocol-specified study visit, it may be necessary to adjust the visit schedule, convert in-clinic visits to telemedicine visits, and/or postpone study procedures until the next available in-clinic study visit. If there is information available from previous visits (ie, laboratory assessments) that requires follow-up procedures or other safety assessments, the Investigator will decide if an on-site visit or home healthcare visit is required or whether the subject's safety can be preserved by other means
- If study participants no longer have access to investigational product, specific procedures should be put in place to ensure delivery of investigational product to subject provided all safety considerations and applicable health authority requirements have been addressed.

### 6.3.2. Subjects Infected by COVID-19

If a subject has had a past documented infection by COVID-19 prior to enrollment in the trial but the subject has recovered and the current diagnostic tests are negative (negative antigen by any diagnostic laboratory kit), the subject can be rescreened if the disease (COVID-19) was mild or moderate, excluding those subjects who experienced hospitalization, severe disease, and/or COVID-19 ARDS.

If a subject has a documented infection by COVID-19 while in the trial:

• The event will be reported as an AE or SAE, depending on the criteria.

The site will follow the guidance provided by health authorities in the treatment of those subjects.

### 7. EFFICACY ASSESSMENTS

# 7.1. Pulmonary Exacerbation

A *pulmonary exacerbation* is defined by having  $\geq 3$  of the following symptoms for at least 48 hours, resulting in a physician's decision to prescribe systemic antibiotics:

- Increased cough
- Increased sputum volume or change in sputum consistency
- Increased sputum purulence
- Increased breathlessness and/or decreased exercise tolerance
- Fatigue and/or malaise
- Hemoptysis

Note: Subjects on chronic macrolide therapy whose only change in therapy is dose or frequency adjustment will not meet the definition of PE.

A severe pulmonary exacerbation is defined as those requiring IV antibacterial drug treatment and/or hospitalization.

Any pulmonary exacerbation in the study after randomization through the end of the 52-week treatment period will be included in the primary endpoint calculation (provided it meets the protocol-defined criteria). A minimum of 14 days must occur between the end date of one pulmonary exacerbation and the start date of the next pulmonary exacerbation. Any exacerbations that occur less than 14 days from the prior exacerbation will not be considered a new exacerbation.

The time to the first pulmonary exacerbation is calculated from the randomization date to the onset date of the first exacerbation. Subjects who do not have an exacerbation at the end of the 52-week treatment period will be censored at the date of Week 52. Subjects who have  $\geq 1$  PE during the study will have event counts and corresponding time to event calculations.

